8.2. Planned Analyses

8.2.1. Interim Analysis

Prior to the final analysis, the primary analysis of the primary endpoint will be conducted, additional interim analyses may be conducted, and the analyses may be submitted to regulatory agencies to seek guidance for the overall clinical development program or for other purposes.

8.2.1.1. DMC Analysis

The DMC will review safety data on a regular basis. The DMC will review safety and efficacy data at the time of the primary analysis.

8.2.2. Primary Analysis

The primary analysis will be performed after all participants have completed Day 11 of Part A of the study or prematurely terminated from the study.

8.2.3. Part A Analysis

The analysis for Part A subjects will be performed after all participants have completed Part A of the study or prematurely terminated from Part A of the study.

8.2.4. Final Analysis

The final analysis will be performed after all participants have completed the study or prematurely terminated from the study, outstanding data queries have been resolved or adjudicated as unresolvable, and the data have been cleaned and finalized. The final analysis will summarize results from Part B of the study.

8.3. Analysis Conventions

8.3.1. Analysis Sets

8.3.1.1. Efficacy

The primary analysis set for efficacy analysis is defined as the Full Analysis Set (FAS), which will include all participants who (1) are randomized into Part A of the study and (2) have received at least 1 dose of study treatment if randomized to 1 of the RDV treatment groups. Participants will be grouped according to the treatment to which they were randomized.

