Study Procedures/ Frequency:	At Screening, after the participant has provided informed consent or assent, demographic and baseline characteristics, medical history, and concomitant medications will be documented. Vital signs including temperature, respiratory rate, and SpO ₂ will be recorded. Radiographic imaging will be performed if not already available. SARS-CoV-2 testing by PCR will be performed; if this testing has been performed within the previous 4 days, no repeat testing is required.

If safety laboratory results from the screening day are not already available, laboratory testing including alanine aminotransferase (ALT) and aspartate aminotransferase (AST), serum creatinine, and creatinine clearance will be performed according to local practice.

In Part A, after screening procedures, eligible participants will be randomized into 1 of the 3 treatment groups in a 1:1:1 ratio to receive:

Treatment Group 1: continued SOC therapy together with IV RDV 200 mg on Day 1 followed by IV RDV 100 mg on Days 2, 3, 4, and 5

Treatment Group 2: continued SOC therapy together with IV RDV 200 mg on Day 1 followed by IV RDV 100 mg on Days 2, 3, 4, 5, 6, 7, 8, 9, and 10

Treatment Group 3: continued SOC therapy

In Part B, after screening procedures, eligible participants will be assigned to receive:

Extension Treatment Group: continued standard of care therapy together with IV RDV 200 mg on Day 1 followed by IV RDV 100 mg on Days 2, 3, 4, 5, 6, 7, 8, 9, and 10 as determined by review of the data. Treatment may be reduced to a total of 5 days following analysis of the data from Part A.

The date of randomization will be considered Day 1 and all participants randomized to receive RDV should receive their initial dose on Day 1.

On study Days 1 through 14 or until discharge, whichever is earlier, 7-point ordinal scale of clinical status, vital signs including respiratory status will be measured and adverse events (AEs) and concomitant medications will be documented. Laboratory testing will be performed according to SOC practice with results for white blood cell count, hemoglobin and/or hematocrit, platelets, creatinine, creatinine clearance, glucose, total bilirubin, ALT, AST, and any SARS-CoV-2 testing being reported to the Sponsor.

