5.1.2. Blinding

Blinding of treatment assignments or data will not be performed in this study.

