6.2. Pretreatment Assessments

6.2.1. Screening Visit

Subjects will be screened within 2 days before randomization and dosing to determine eligibility for participation in the study.

- Obtain written informed consent or assent (age ≥ 12 to < 18 , where locally and nationally approved)

After the informed consent the following assessments are performed to determine eligibility requirements as specified in the inclusion and exclusion criteria:

- Focused medical history including the following information (eg, date of first symptoms, overall symptoms, exposure source, demographics, baseline characteristics, allergies and medical history)
- Review and record medications and therapies for this current illness
- Counsel subjects to use adequate birth control methods required during the trial to avoid pregnancy
- Targeted physical examination including, vital signs (heart rate, temperature, blood pressure), body weight, and height
- Documentation of respiratory status:

Respiratory Rate

- Oxygen supplementation: room air, low flow O₂ (L/min and %), high flow O₂ (L/min and %), CPAP/BIPAP (FiO₂ or %), mechanical ventilation (FiO₂ or %), ECMO

Oxygenation: SpO₂ or PaO₂

Radiographic findings

- Obtain blood samples if not done in the preceding 48 hours for creatinine, creatinine clearance, ALT and AST
- Pregnancy test (for women of childbearing potential)
- Record any serious adverse events and all adverse events related to protocol-mandated procedures occurring after signing of the consent (or assent) form.

Study subjects who qualify should be immediately randomized. Randomization and dosing should occur on the same day if possible.

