6.2.2. Baseline/Day 1 Assessments

The following evaluations are to be completed at the Day 1 visit. The investigator must have confirmed eligibility before proceeding with randomization on the Day 1 visit. If the screening and Day 1 visits occur within 24 hours, no procedures need to be repeated. Participants must complete the following assessments before being administered study drug:

- Physical examination including, vital signs (heart rate, temperature, blood pressure, and body weight)
- Documentation of respiratory status:

Respiratory rate

— Oxygen supplementation: room air, low flow O₂ (L/min and %), high flow O₂ (L/min and %), CPAP/BIPAP (FiO₂ or %), mechanical ventilation (FiO₂ or %), ECMO

Oxygenation: SpO₂ or PaO₂

Radiographic findings (if available)

- Review AEs and document concomitant medications
- Obtain blood samples for white blood cell count, hemoglobin and/or hematocrit, platelets, creatinine and creatinine clearance, glucose, total bilirubin, ALT, AST

- SARS-CoV-2 Testing: Collect nasopharyngeal swab sample for subjects/sites participating in this portion of the study
- Review Ordinal Scale (Section 6.9)

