8.3.2. Data Handling Conventions

CCI

Laboratory data that are continuous in nature but are less than the lower limit of quantitation or above the upper limit of quantitation, will be imputed to the value of the lower or upper limit plus or minus 1 significant digit, respectively (eg, if the result of a continuous laboratory test is < 20, a value of 19 will be assigned).

Missing data can have an impact upon the interpretation of the trial data. In general, values for missing data will not be imputed. However, a missing pre-treatment laboratory result would be treated as normal (ie, no toxicity grade) for the laboratory abnormality summary.

All available data for participants that do not complete the study will be included in data listings.

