8.5. Efficacy Analysis

8.5.1. Primary Analysis

The primary endpoint will be analyzed using a proportional odds model including baseline clinical status as a covariate. Each RDV group will be compared to the SOC group. The null hypothesis being tested is whether the odds of improvement on the ordinal scale is the same for the SOC group and either RDV group (ie, whether the common odds ratio is equal to 1). The odds ratio and 95% confidence interval for each comparison will be provided.

The proportion of subjects in each category will be summarized by treatment group. The validity of the proportionality assumption will be evaluated.

If a participant is discharged prior to Day 11, the Day 11 ordinal scale category is considered to be not hospitalized. If a participant dies prior to Day 11, the Day 11 ordinal scale category is considered to be death. Every effort will be made to obtain clinical status data for all subjects prior to discharge.

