2.1.2. Primary Analysis

The primary analysis was performed after data were available from participants in Part A of the study who completed 11 days or prematurely terminated from Part A of the study on or prior to Day 11. This analysis was described in the Part A Primary Analysis SAP dated 25 May 2020. This is considered as the primary analysis of the study, but most of the analyses were repeated in the Part A Final Analysis.

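### The primary efficacy set drops undosed participants from the remdesivir arms only, a one-sided post-randomization exclusion in an open-label trial; probably small, and cheap to remove

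*Protocol*

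**What the plan says.** Protocol 8.3.1.1 defines the Full Analysis Set (FAS) as the primary efficacy set. Participants must be randomized into Part A and must "have received at least 1 dose of study treatment if randomized to 1 of the RDV treatment groups". They are then grouped by the arm to which they were randomized. SOC participants need only be randomized.

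The surrounding text bears on how often the condition could bite:

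- Protocol 5.1.2: "Blinding of treatment assignments or data will not be performed in this study".
- Protocol synopsis, study procedures: "The date of randomization will be considered Day 1 and all participants randomized to receive RDV should receive their initial dose on Day 1".
- Protocol 6.2.1 is softer: "Randomization and dosing should occur on the same day if possible".
- Protocol 6.2.2: "The investigator must have confirmed eligibility before proceeding with randomization on the Day 1 visit".
- Protocol 3.4 and 5.3: RDV ends at discharge.

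On outcomes, Protocol 8.5.1 states "If a participant is discharged prior to Day 11, the Day 11 ordinal scale category is considered to be not hospitalized", assigns death in the same way, and attaches no dosing condition to either rule. Protocol 8.3.2 adds "In general, values for missing data will not be imputed"; part of that section is redacted.

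Neither document defines an all-randomized efficacy set for Part A. The SAP supplied covers Part B. Of the Part A primary analysis its section 2.1.2 says only "This analysis was described in the Part A Primary Analysis SAP dated 25 May 2020", and that plan is not among the documents.

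**The concern.** Whether an RDV participant is dosed is settled after randomization, with the assignment known to patient and staff. Refusal, a change in condition, or discharge before the first dose would each remove an RDV participant from the FAS. An SOC participant with the same course stays in. If the reason for non-dosing is related to outcome, the arms no longer have the same expected mix of prognoses, even under no drug effect.

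The direction is not fixed. Losing participants who were about to do badly favours RDV; losing early discharges favours SOC. Both RDV arms are exposed, so both primary comparisons are. Without undosed counts and reasons by arm, a reader cannot judge how far the odds ratio has moved.

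**Working it through.** **Inputs.** From Protocol 8.9: SOC Day 11 distribution for categories 1 to 7 of 0.5, 2.5, 7, 8, 15, 27 and 40%; 200 per arm; design odds ratio 1.8; two-sided alpha 0.05. The share undosed is not stated; I use 1%, 2% and 5% of an RDV arm (2, 4 and 10 of 200).

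**The plan's own figure.** With p̄ the average of the SOC distribution and that distribution shifted by an odds ratio of 1.8, the information for the log odds ratio implied by the formula in Protocol 8.9 is

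I = (400/12) × (1 − Σp̄ᵢ³) = 33.33 × (1 − 0.1248) = 29.17.

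Then z = ln(1.8) × √29.17 = 0.5878 × 5.401 = 3.175, and power = Φ(3.175 − 1.960) = 88.8%. The stated figure of more than 85% is reproduced.

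**Effect of the exclusion under no drug effect.** Start with an RDV arm that has the SOC distribution. Remove a fraction f with Day 11 distribution u, so the remaining arm is (p − f·u)/(1 − f). Fit a two-group proportional odds model to the cell probabilities by maximum likelihood, set z = ln(OR) × √I with I as above, and take P(|N(z,1)| > 1.96) as the two-sided error. The upper tail is the error in favour of RDV, nominally 2.5%. I is computed at 200 per arm; using 200(1 − f) for the RDV arm changes the error by at most 0.2 percentage points.

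One case by hand: f = 5%, with the undosed twice as likely to be in categories 1–5 (66% against 33%). Of 10 undosed, 6.6 come from categories 1–5 and 3.4 from categories 6–7. The arm of 66 and 134 becomes 59.4 and 130.6. The odds of being in categories 6–7 go from 134/66 = 2.03 to 130.6/59.4 = 2.20, a ratio of 1.08 at that cut. At the discharge cut the ratio is 1.04. The common odds ratio over all cuts is 1.06.

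Each cell gives OR; two-sided error; error in favour of RDV.

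| Who is undosed | 1% undosed | 2% undosed | 5% undosed |
|---|---|---|---|
| Same as the rest of the arm | 1.00; 5.0%; 2.5% | 1.00; 5.0%; 2.5% | 1.00; 5.0%; 2.5% |
| Twice as likely in categories 1–4 (36% vs 18%) | 1.01; 5.0%; 2.7% | 1.01; 5.1%; 2.9% | 1.03; 5.3%; 3.7% |
| Twice as likely in categories 1–5 (66% vs 33%) | 1.01; 5.0%; 2.9% | 1.02; 5.2%; 3.3% | 1.06; 6.1%; 5.0% |
| Twice as likely discharged (80% vs 40%) | 0.99; 5.1%; 2.1% | 0.97; 5.3%; 1.8% | 0.93; 6.7%; 1.0% |
| Extreme: all from categories 1–4 | 1.03; 5.3%; 3.5% | 1.06; 6.1%; 4.9% | 1.15; 12.3%; 12.0% |
| Extreme: all discharged | 0.98; 5.1%; 1.9% | 0.96; 5.6%; 1.5% | 0.90; 8.8%; 0.6% |

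The extreme rows are bounds, not expectations. About 0.18 × 200 = 36 participants per arm are expected in categories 1–4, so the 12.3% figure needs 10/36 = 28% of them never to have been dosed.

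**Cost of analysing everyone.** Suppose undosed RDV participants have SOC outcomes, so the RDV arm is (1 − f) × shifted + f × SOC. The odds ratio of 1.8 becomes 1.78, 1.77 and 1.74 at 2%, 3% and 5% undosed, and z becomes 3.109, 3.075 and 3.009. Power is 87.5%, 86.8% and 85.3%.

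**The case against.** The best defence is that very few participants can be affected. They are inpatients needing care, eligibility is confirmed before randomization, and dosing is expected the same day. No passage supports a 2–5% undosed rate. At 1%, moderate selection moves the odds ratio by little more than 1% and leaves the error at or below 5.1%. Discharge between randomization and a same-day first dose is allowed by the text but not likely. This stands, and it is why the effect is called probably small. It does not show that the number is negligible, because nothing in the documents reports it.

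Two points concern the calculation. The planned model adjusts for baseline clinical status and mine does not, so selection acting through baseline status would be partly absorbed; how much cannot be known here. Also, an SOC participant who leaves with no Day 11 status may drop out of the model too, depending on a missing-data rule that is partly redacted. The practical asymmetry may therefore differ from the formal one. But missing outcomes can occur in any arm, whereas the FAS rule removes RDV participants even when their Day 11 status is known.

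Finally, the Part A SAP may contain an all-randomized sensitivity analysis, and Part A has already been analysed (SAP 2.1.2 and 2.1.3), so redefining the primary set now would be post hoc. Both points limit the remedy. Neither changes the fact that the protocol names this set as primary.

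**Conclusion.** The concern holds and should be fixed. The one-sided exclusion follows directly from Protocol 8.3.1.1, and the open allocation from 5.1.2. Its size rests on assumptions: 2–5% undosed, no drug effect, the Protocol 8.9 distribution, and no baseline covariate. Under moderate selection the odds ratio lies between 0.93 and 1.06 and the two-sided error between 5.1% and 6.7%; the error in favour of RDV reaches at most 5.0% against 2.5%. If non-dosing is unrelated to outcome, there is no bias. This is small beside a design odds ratio of 1.8 and would not by itself overturn a clear result. It could matter for a borderline one, and it is avoidable.

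**What to change.** In Protocol 8.3.1.1 and the Part A SAP, define the primary efficacy set as all participants randomized into Part A, analysed as randomized. Score undosed RDV participants from their Day 11 status, discharge or death by the existing 8.5.1 rules, exactly as for SOC, and state one rule for missing Day 11 status that applies to every arm. Keep the dosed set as a supportive analysis. Report the number undosed and the reasons by arm; SAP 4.1 already plans a never-treated count for Part B.

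Since the Part A analysis has been run, present the all-randomized result beside it, labelled as supplementary, unless the Part A SAP already planned it.

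The cost is a wording change, status collection for a handful of participants, and one extra model run. The drawback is slight dilution: power falls from 88.8% to 85.3% at 5% undosed, if the undosed have SOC outcomes. Participants who withdrew consent with no later status cannot be recovered this way.

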8.3.1.2. Safety

The primary analysis set for safety analyses is defined as the Safety Analysis Set, which will include all participants who (1) are randomized into the study and (2) have received at least 1 dose of study treatment if randomized to 1 of the RDV treatment groups. Participants will be grouped according to the treatment which they received.

8.3.1.3. Extension Analysis Set

The Extension Analysis Set will include participants who have received at least 1 dose of RDV in Extension Treatment Group. This analysis set will be used for both the safety and efficacy evaluations for participants enrolled in Part B.

8.3.2. Data Handling Conventions

CCI

Laboratory data that are continuous in nature but are less than the lower limit of quantitation or above the upper limit of quantitation, will be imputed to the value of the lower or upper limit plus or minus 1 significant digit, respectively (eg, if the result of a continuous laboratory test is < 20, a value of 19 will be assigned).

Missing data can have an impact upon the interpretation of the trial data. In general, values for missing data will not be imputed. However, a missing pre-treatment laboratory result would be treated as normal (ie, no toxicity grade) for the laboratory abnormality summary.

All available data for participants that do not complete the study will be included in data listings.

8.4. Demographic and Baseline Characteristics Analysis

Demographic and baseline measurements will be summarized using standard descriptive methods. Demographic summaries will include sex, race/ethnicity, and age. For categorical demographic and baseline characteristics, a Cochran Mantel Haenszel test will be used to compare treatment groups. For continuous demographic and baseline characteristics, a Wilcoxon rank sum test will be used to compare treatment groups.

8.5. Efficacy Analysis

8.5.1. Primary Analysis

The primary endpoint will be analyzed using a proportional odds model including baseline clinical status as a covariate. Each RDV group will be compared to the SOC group. The null hypothesis being tested is whether the odds of improvement on the ordinal scale is the same for the SOC group and either RDV group (ie, whether the common odds ratio is equal to 1). The odds ratio and 95% confidence interval for each comparison will be provided.

The proportion of subjects in each category will be summarized by treatment group. The validity of the proportionality assumption will be evaluated.

If a participant is discharged prior to Day 11, the Day 11 ordinal scale category is considered to be not hospitalized. If a participant dies prior to Day 11, the Day 11 ordinal scale category is considered to be death. Every effort will be made to obtain clinical status data for all subjects prior to discharge.

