4.2. Inclusion Criteria

Subjects must meet all of the following inclusion criteria to be eligible for participation in this study:

- 1) Willing and able to provide written informed consent (participants ≥ 18 years of age) or assent (participants ≥ 12 and < 18 years of age) prior to performing study procedures. For participants ≥ 12 and < 18 years of age, a parent or legal guardian willing and able to provide written informed consent prior to performing study procedures
- 2) Aged ≥ 18 years (at all sites), or aged ≥ 12 and < 18 years of age weighing ≥ 40 kg (where permitted according to local law and approved nationally and by the relevant institutional review board [IRB] or independent ethics committee [IEC])
- 3) SARS-CoV-2 infection confirmed by PCR ≤ 4 days before randomization
- 4) Currently hospitalized and requiring medical care for COVID-19
- 5) SpO₂ $> 94\%$ on room air at screening
- 6) Radiographic evidence of pulmonary infiltrates
- 7) Men and women of childbearing potential who engage in heterosexual intercourse must agree to use protocol specified method(s) of contraception as described in [Appendix 3](#).

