8.9. Sample Size

The sample size computation is based on an assumed distribution of the 7-point ordinal scale on Day 11 for the SOC treatment group. The odds ratio represents the odds of improvement in the 7-point ordinal scale for an RDV treatment group relative to the SOC treatment group. The sample size needed to detect a given odds ratio for a 1:1 randomization using a 2-tailed test at level α is given by:

$$12 (z_{\alpha/2} + z_{\beta})^2 / \theta^2 (1 - \sum_{i=1}^7 \rho_i^3)$$

Where θ is the log odds ratio, ρ_i is the overall probability (combined over both treatment groups) of being in the i th category of the ordinal outcome, and $z_{\alpha/2}$ and z_{β} are the $1 - \alpha/2$ and β quantiles of the standard normal distribution {Whitehead 1993}.

A sample size of 600 participants (200 in each group) achieves > 85% power to detect an odds ratio of 1.8 using a two-sided significance level of 0.05 for comparing each RDV group (n = 200) to standard of care group (n = 200). In this sample size calculation, it is assumed that the probability distribution of the ordinal scale at Day 11 for Treatment Group 3 is as follows:

1. Death, 0.5%
2. Hospitalized, on invasive mechanical ventilation or ECMO, 2.5%
3. Hospitalized, on non-invasive ventilation or high flow oxygen devices, 7%
4. Hospitalized, requiring low flow supplemental oxygen, 8%
5. Hospitalized, not requiring supplemental oxygen - requiring ongoing medical care (COVID-19 related or otherwise), 15%
6. Hospitalized, not requiring supplemental oxygen - no longer requires ongoing medical care (other than per protocol RDV administration), 27%
7. Not hospitalized, 40%

The sample size calculation was done using software PASS (Version 14.0).

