5.2. Other Baseline Characteristics

The following baseline disease characteristics will be summarized using descriptive statistics:

- Clinical status (7-point ordinal scale)
- Duration of hospitalization prior to first dose of RDV
- Duration of symptoms prior to first dose of RDV
- AST
- ALT
- Oxygen support status based on the 7-point ordinal scale (low-flow oxygen, room air)
- Region (North America, Europe, Asia)

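### The primary model adjusts only for baseline clinical status, which entry criteria probably concentrate at score 5; prespecified adjustment for age and symptom duration would add modest efficiency at little cost

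*Protocol*

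**What the plan says.** Protocol 8.5.1 defines the primary analysis: "The primary endpoint will be analyzed using a proportional odds model including baseline clinical status as a covariate". It continues: "Each RDV group will be compared to the SOC group". Protocol 3.2 and 5.1.1 both say that randomization is not stratified.

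Eligibility (Protocol 4.2) limits entry to hospital patients who need care for COVID-19 and whose saturation is above 94% "on room air at screening". On the scale in Protocol 6.9 that description fits score 5.

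Other baseline information is available. The screening history in Protocol 6.2.1 covers "date of first symptoms, overall symptoms, exposure source, demographics, baseline characteristics". The supplied SAP, which covers Part B only, lists "Duration of symptoms prior to first dose of RDV" among the baseline characteristics (5.2) and uses age and region as subgroup factors (3.4.1).

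Protocol 8.4 plans tests comparing baseline characteristics between groups but attaches no consequence for the primary model. Protocol 8.9 says that 200 per group "achieves > 85% power to detect an odds ratio of 1.8 using a two-sided significance level of 0.05 for comparing each RDV group".

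**The concern.** A covariate helps only if it varies and predicts the outcome. If most participants share one baseline score, the single planned covariate can separate few of them. Age and time since symptom onset could plausibly predict Day 11 status: the assumed SOC distribution puts 27% + 40% = 67% in scores 6 and 7, so the endpoint turns largely on discharge and on no longer needing care. Both variables are recorded before treatment, so using them needs no new data.

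Two things are at stake. The first is efficiency: in a proportional odds model, adjusting for prognostic covariates raises power for the same number of participants. The second is chance imbalance. Nothing in the randomization balances these factors within the trial, and if the baseline tests in Protocol 8.4 showed a difference, any response in the model would be post hoc in an open-label study.

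**Working it through.** **Inputs from Protocol 8.9.** SOC distribution at Day 11 for scores 1 to 7: 0.5 / 2.5 / 7 / 8 / 15 / 27 / 40%. Odds ratio 1.8, two-sided alpha 0.05, 200 per group, so N = 400 per comparison.

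**Step 1: reproduce the stated power.** The printed formula is N = 12(z_α/2 + z_β)² / [θ²(1 − Σρᵢ³)], with N the total of the two groups.

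- θ = ln 1.8 = 0.5878.
- Shifting the SOC distribution by an odds ratio of 1.8 gives 0.3 / 1.4 / 4.1 / 5.1 / 10.6 / 24.0 / 54.5%.
- The means of the two distributions are ρ = 0.0039, 0.0196, 0.0556, 0.0653, 0.1281, 0.2549, 0.4727, so Σρᵢ³ = 0.1248 and 1 − Σρᵢ³ = 0.8752.
- Power = Φ(√(400 × 0.8752 / 12) × 0.5878 − 1.960) = Φ(3.175 − 1.960) = 88.8%.

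This meets the claim of more than 85% (85% needs N = 357). The formula contains no covariate term.

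**Step 2: power with added covariates.** The documents give no prognostic strength, so it is varied. The added covariates are summarised as one standard-normal score with log-odds SD τ. Cut-points are recalibrated so that the SOC distribution stays as stated. The conditional odds ratio is set so that a proportional odds fit without the score gives 1.8 (the marginal odds ratio). Power is Φ(θ/SE − 1.960), with SE from the Fisher information at 200 per group.

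Without a covariate, SE = 0.1873 and power = Φ(0.5878/0.1873 − 1.960) = 88.1%. This is the comparator below; it differs from 88.8% only in the variance approximation.

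| τ | Conditional OR | ln OR | SE | ln OR / SE | Power | Gain over 88.1% |
|---|---|---|---|---|---|---|
| 0.3 | 1.82 | 0.599 | 0.1883 | 3.18 | 88.9% | 0.8 |
| 0.5 | 1.86 | 0.618 | 0.1898 | 3.26 | 90.3% | 2.2 |
| 0.8 | 1.94 | 0.662 | 0.1932 | 3.43 | 92.9% | 4.8 |
| 1.0 | 2.01 | 0.699 | 0.1958 | 3.57 | 94.6% | 6.5 |

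Proportional odds cannot hold exactly both with and without the score, so the marginal odds ratio can be summarised in more than one way. Another summary gives 89.9% at τ = 0.5 and 93.7% at τ = 1.0, so the table is good to about one point.

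**Step 3: is the planned covariate uninformative?** Step 2 compares with no informative covariate, not with the planned model. Suppose 5 to 15% of participants are off the modal score and that difference carries an odds ratio of 4 to 8 (both assumed). Adjusting for baseline status alone then gives about 89 to 93%, against 88.1%. In that case the plan already captures a gain of similar size, and the further gain from age and symptom duration is smaller than the table shows.

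**Step 4: chance imbalance.** With 200 per arm, the difference between arms in the mean of a standardised score has standard error √(2/200) = 0.10. A one-standard-error imbalance therefore shifts an unadjusted log odds ratio by roughly 0.10 × τ: 0.03 at τ = 0.3 and 0.10 at τ = 1.0, against a standard error of 0.187. This is one source of the efficiency loss in step 2, not an addition to it.

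**The case against.** A reader might infer that the trial is underpowered or that its power figure is wrong. The documents do not support that. The calculation never relied on adjustment, and it reproduces. The natural reading of 1.8 in a formula without covariates is a marginal odds ratio. Only if 1.8 were meant as conditional on a strong prognostic score would power without adjustment fall clearly below 85% (about 76 to 78% at τ = 1.0, against 85.8% adjusted), and the protocol does not say that it was.

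A reader might also take baseline status to be constant. Eligibility is judged at screening, up to 2 days before randomization. Protocol 4.3 excludes only mechanical ventilation as a form of respiratory support. The recovery endpoints in Protocol 3.1 provide for baseline scores 2 through 6, and SAP 3.4.1 has a low-flow oxygen subgroup. Concentration at score 5 is likely; near-constancy is not shown.

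Third, the supplied SAP is not evidence about the Part A model. SAP 3.3 plans no covariates because Part B has no formal testing, and SAP 6.1 leaves the primary endpoint to Part A. SAP 2.1.2 cites a Part A Primary Analysis SAP dated 25 May 2020, which may already contain adjusted analyses.

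Fourth, randomization at 200 per arm already gives valid inference, and adjustment does nothing about bias from open-label assessment.

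Fifth, adjustment has costs. Protocol 8.3.2 generally leaves missing values unimputed, so a missing onset date would drop a participant from the model. Region categories appear only in the Part B SAP. Each added term carries its own proportional odds assumption.

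All five points stand. They limit the size of the gain, the confidence and the form of the fix. They do not change the fact that the model in Protocol 8.5.1 leaves recorded baseline information unused.

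**Conclusion.** The point holds as a modest, inexpensive improvement, not as an error. The stated power is correct at 88.8% without covariates. At a marginal odds ratio of 1.8, the forgone gain is about 1 to 2 points for weak to moderate covariates and about 5 to 6.5 points for strong ones.

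This rests on an assumed prognostic strength for age and symptom duration, and on baseline status carrying little information. If baseline status is informative, the gain over the planned model is smaller. Confidence is moderate because the Part A SAP was not available.

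**What to change.** In Protocol 8.5.1, and in the Part A SAP if it does not already do this, specify the model as treatment + baseline clinical status + age (continuous) + symptom duration before Day 1. Count symptom duration to Day 1, the randomization date, rather than to first dose as in SAP 5.2, because the SOC group has no first dose. State a simple rule for missing onset dates, for example median imputation blind to arm, so that nobody is dropped. Add region only if its categories are defined for Part A and none is sparse. Label the odds ratio as conditional, say whether the planning value of 1.8 is marginal or conditional, and keep the current model as a sensitivity analysis.

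SAP 2.1.2 reports that the primary analysis has already been performed. If the Part A SAP did not prespecify such a model, an adjusted result produced now should be reported as a labelled sensitivity analysis and should not replace the primary result.

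The cost is a few sentences and one more model fit per comparison, with no added participants or procedures. The downsides are small: a missing-covariate rule is needed, and the conditional odds ratio is somewhat larger than the marginal one (about 1.82 to 2.01 against 1.80), so the two must not be compared as if they were the same quantity.
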